2.1. Primary Objective

The principal endpoint of this screening inhaled allergen challenge protocol will be to identify those subjects who experience a 15% or greater drop in FEV₁ from baseline within 3-10 hours after the EPR.

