3. INVESTIGATIONAL PLAN

3.1. Study Design

Type of Design: open-label, single arm study

This will be a non-blinded study to identify mild allergic asthmatics with measurable LPR to inhaled cat hair allergen extract. The principal endpoint will be the presence of a LPR, defined as a decline in FEV1 of $\geq 15\%$ from baseline values 3-10 hours after the onset of the EPR (which typically occurs within 30 minutes of allergen challenge).

Prior to enrollment, subjects will undergo a screening visit to establish eligibility (part of a separate screening protocol IRB#98-0799). Study visits will consist of a baseline visit to determine baseline values for study endpoints (Visit 1), a pre-allergen challenge visit to determine pre-challenge values for study endpoints (Visit 2), an allergen challenge visit (Visit 3), a visit 24 hours post-challenge to evaluate symptoms (Visit 4), and a final study discontinuation visit 5-10 days following allergen challenge.

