3.3. Study Population

Inclusion Criteria:

1. Age range 18-45 years, inclusive
2. FEV₁ of at least 80% of predicted and FEV₁/FVC ratio of at least 0.7 (without use of bronchodilator medications for 8 hours or long acting beta agonists for 24 hours), consistent with lung function of persons with no more than mild intermittent or mild persistent asthma.
3. Physician diagnosis of asthma
4. Allergic sensitization to cat hair extract as demonstrated by positive immediate skin prick test response or serum cat IgE >0.35 kU/L.
5. Negative pregnancy test for females who are not s/p hysterectomy with oophorectomy or who have been amenorrheic for 12 months or more.
6. Oxygen saturation of >94% and blood pressure within the following limits: Systolic between 150-90 mmHg and Diastolic between 90-60 mmHg.

Exclusion Criteria:

1. Clinical contraindications:
 - a. Any chronic medical condition considered by the PI as a contraindication to participation in the study including significant cardiovascular disease, diabetes, chronic renal disease, chronic thyroid disease, history of chronic infections or immunodeficiency.
 - b. Physician directed emergency treatment for an asthma exacerbation within the preceding 12 months.
 - c. Exacerbation of asthma more than 2x/week which could be characteristic of a person of moderate or severe persistent asthma as outlined in the current NHLBI guidelines for diagnosis and management of asthma.
 - d. Daily requirements for albuterol due to asthma symptoms (cough, wheeze, chest tightness) which would be characteristic of a person of moderate or severe persistent asthma as outlined in the current NHLBI guidelines for diagnosis and management of asthma (not to include prophylactic use of albuterol prior to exercise).
 - e. Viral upper respiratory tract infection within 4 weeks of challenge.
 - f. Any acute infection requiring antibiotics within 6 weeks of challenge or fever of unknown origin within 6 weeks of challenge.
 - g. Severe asthma

- h. Mental illness or history of drug or alcohol abuse that, in the opinion of the investigator, would interfere with the participant's ability to comply with study requirements.
 - i. Cigarette smoking >1 pack per month

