4.8. Criteria for Screen Failure (for Anakinra Studies)

Participants who do not fulfill the following safety criteria will be considered screen failures and will not be eligible for enrollment into the Anakinra study protocols:

1. Less than or equal to 40% decrease in FEV₁ or FVC from pre-challenge values following EPR or the LPR to cat hair allergen (the target endpoint is a $\geq 20\%$ decrease in FEV₁ from baseline during the EPR and a $\geq 15\%$ decrease in FEV₁ from baseline during the LPR); 2) If albuterol is employed as rescue, FEV₁ must recover to within 90% of baseline value within 20 minutes; 3) Oxygen saturation should remain $\geq 93\%$ throughout the challenge period and must be no lower than 2% of baseline measure;
2. Albuterol for rescue therapy should be required no more than three times within the first hour after challenge
3. Albuterol for rescue therapy should be required no more than three times within 12 hours of discharge.
4. FEV₁ should return to within 90% of baseline value at the study discontinuation visit which occurs within 10 days after allergen challenge.
5. Subjects who require more than 1 dose of oral corticosteroid (prednisone 60 mg) to treat an asthma exacerbation associated with inhalation challenge will be considered screen fails and will not continue.

Subjects who are withdrawn for medical concerns related to the study, such as but not limited to prolonged decreased FEV₁ or persistent wheezing, will be followed by study physicians until resolution of these events. As this is a screening protocol, these subjects will not be replaced.

If following all doses of inhaled allergen challenge a participant remains asymptomatic and FEV₁ drops <10% at the completion of the challenge, that participant will be considered a screen failure and will be monitored for 2 hours post challenge. The participant will be discharged following post-challenge venipuncture with rescue medications, including albuterol with aerochamber and oral prednisone 60 mg, instructions for use of these medications in the event of symptoms related to bronchoconstriction, and contact information for the on-call physician. Subject will resume the protocol beginning with Study visit 4 detailed above.

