The FEV₁ will be measured prior to and 10 minutes after each aerosol inhalation. Starting with the control (saline diluent) solution, increasing concentrations of allergen will be inhaled at 10-minute intervals starting with 0.31 BAU/ml. The FEV₁ measurement obtained after inhalation of the control solution (saline) will be considered the baseline value. If the FEV₁ has declined by less than 10% of baseline after a given concentration of allergen is inhaled, the next higher concentration of allergen will be given. If after inhalation of an allergen dose, the FEV₁ declines by $\geq 10\%$ but $< 20\%$ from the baseline FEV₁ measurement, spirometry will be repeated every 5 minutes for 15 minutes or until a clear nadir in the decline has been reached. If the nadir after 15 minutes is a decline in FEV₁ of less than 10% of baseline, the next higher concentration of allergen will be given. If, however, the nadir after 15 minutes is a decline in FEV₁ $\geq 10\%$ but $< 20\%$ from the baseline measurement, the previous allergen dose will be repeated. To prioritize the safety of subjects and to prevent severe or precipitous decline in lung function, decisions to repeat doses of allergen (rather than escalate dosing) or perform additional spirometry measurements will be made in real time at the discretion of the supervising physician, who will be physically present throughout the allergen challenge procedure. Once a decline in FEV₁ of $\geq 20\%$ is reached, the challenge will be stopped. These activities are summarized in **Figure 1**. Once the challenge is stopped, FEV₁ will be monitored every 10 minutes for the first hour, then every 30 minutes until 2 hours post-challenge, and then hourly until 10 hours after the last allergen dose.

[figure not shown]

Figure 1. Inhaled allergen challenge schematic.

*At discretion of supervising physician

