6 STATISTICAL CONSIDERATION

6.1. Primary Endpoint

The principal endpoint of this screening inhaled allergen challenge protocol will be to identify those subjects who experience a 15% or greater drop in FEV₁ from baseline within 3-10 hours after the EPR.

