6.2. Secondary Endpoint

In addition to identifying subjects for participation in the planned studies of Anakinra vs placebo for mitigating features of asthma exacerbation, the additional purpose of this study is to determine if IL-1 β concentrations in the sputum at baseline before challenge are predictive of key asthma outcomes following inhaled allergen challenge

- 1) Baseline sputum IL-1 β concentration (pg/mL)
- 2) Asthma outcomes following allergen challenge as measured by:
 - a). maximum drop in %FEV1 during LPR
 - b). Change in methacholine reactivity from baseline pre-allergen measurement to 24 hours after allergen challenge.
 - c). exhaled nitric oxide (eNO) level
 - d). induced sputum:
 - i. Granulocyte (neutrophils/eosinophils) numbers and percentages
 - ii. Mucins (secretion of MUC5AC and MUC5B determined by Western blot and ELISA)

Exploratory Endpoints

Additionally, as exploratory endpoints, we will assess the effects of allergen challenge on markers of systemic inflammation and changes in inflammatory gene expression as described below:

- a). **venipuncture** for assessment of systemic inflammatory markers (CBC with differential for absolute neutrophil count and absolute eosinophil count), pro-inflammatory cytokine levels such as IL-1 β , IL-6, IL-8).
- b). **nasal ELF** for assessment of inflammatory mediators associated with allergen-induced airway inflammation.
- c). **gene array analysis** from blood and induced sputum at the baseline visit, again on the day of the challenge and, finally, at 24 hours post challenge. To identify signaling pathways potentially impacted by allergen challenge, we will use Nanostring® technology to measure differential expression of a panel of 594 immunology-related genes. This will be accomplished by collecting and isolating peripheral blood mononuclear cells from venous blood samples collected before allergen challenge, during allergen challenge, and 24 hours after allergen challenge.
- d). **heart rate variability** measurement via commercially-available monitor (Space Labs, Inc). We will identify if specific cardiac changes occur during allergen-induced asthma exacerbation.

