6.3. Statistical Methods

Our analytical plan was developed with [name], the biostatistician for the CEMALB who will oversee all statistical analysis. In all analyses, criterion for significance will be $p \leq 0.05$. All statistical estimates will be tabulated along with the corresponding confidence intervals.

Our primary endpoint is identification of subjects who achieve a $\geq 15\%$ fall in FEV₁ during hours 3-10 following allergen challenge. We will subtract the pre-allergen challenge %FEV₁ value from the post-allergen %FEV₁ value to make this determination.

For analysis of secondary endpoints, we will first use linear regression to determine if there is a linear relationship between baseline sputum IL-1 β concentration (pg/mL) and asthma outcomes (maximum fall in %FEV1 during LPR, methacholine reactivity defined by the dose required to produce a $\geq 20\%$ drop in FEV1, sputum granulocyte content both in terms of % of total cell count and cells/mg of sputum, exhaled nitric oxide concentration) following allergen challenge, adjusting for potential confounders. The point estimate and confidence interval will be reported for the effect of baseline sputum IL-1 β on asthma outcomes. If the normality assumption is violated or there exists a non-linear relationship, we will calculate the Spearman correlation coefficient between baseline sputum IL-1 β concentration and asthma outcomes.

For analysis of exploratory endpoints, we will use two sample comparison tests to compare systemic inflammatory markers and gene expression levels before and after allergen challenge. We will use two-sample t tests or Mann Whitney U tests depending on whether the normality assumption is met. The point estimate and confidence interval will be reported for mean changes. We will transform the data to achieve normality if needed. HRV endpoints are exploratory, as we do not know if there will be changes during bronchospasm.

As we have considered additional individuals in our sample size calculation, we do not anticipate missing data will be a major issue affecting our study power.

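### Section 6.3 decides late-phase response status by subtracting two undefined %FEV1 values; unless %FEV1 means percent of post-saline baseline, this is not the protocol's endpoint of a 15% or greater fall from baseline

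*Combined protocol and SAP*

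**What the plan says.** The definition is on a relative scale wherever it appears.

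- Section 2.1 looks for subjects who "experience a 15% or greater drop in FEV₁ from baseline within 3-10 hours after the EPR". Section 6.1 repeats this ("from baseline within 3-10 hours after the EPR").
- Section 3.1 counts the decline "from baseline values 3-10 hours after the onset of the EPR".
- Section 4.8 gives the target for the anakinra studies as a 15% or greater "decrease in FEV₁ from baseline during the LPR", and section 9.5 restates it.
- Section 5.1 fixes the reference for the challenge: the FEV1 "measurement obtained after inhalation of the control solution (saline) will be considered the baseline value".

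Section 6.3 first restates the endpoint as a fall of at least 15%, then says how to establish it: "We will subtract the pre-allergen challenge %FEV₁ value from the post-allergen %FEV₁ value to make this determination". The synopsis carries the same sentence. Neither place defines %FEV1, divides by baseline, ties the pre-allergen value to the post-saline measurement, or says which post-allergen value in the window is used.

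The same undefined term appears in the secondary outcome in section 6.2, "maximum drop in %FEV1 during LPR", and in the sample size text of section 6.4.

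**The concern.** A percentage fall from baseline and a difference between two percentages are the same quantity only if both percentages have baseline as their denominator. The documents express FEV1 as a percentage in two ways. The recovery criteria in sections 4.8 and 9.5 use percent of baseline. The eligibility floor in section 3.3, "FEV₁ of at least 80% of predicted", uses percent predicted, and sections 5.1 and 9.4 apply that floor again just before the challenge.

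Percent predicted is a credible reading of the subtraction. On the percent-of-baseline scale the value being subtracted would be 100 for every subject, whereas the sentence reads as if each subject has a pre-challenge value of their own. The spirometry required just before the challenge supplies one, judged as percent predicted.

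LPR status is the sole primary endpoint, and under section 6.4 screening ends once 25 LPR subjects have been found. If an analyst applied 6.3 literally to percent-predicted values, a subject could meet the definition in 6.1 and 4.8 and fail the calculation in 6.3, or the reverse. The regressions of the largest LPR drop on baseline sputum IL-1β would also have an outcome that carries baseline lung function within it.

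**Working it through.** **Inputs.** The threshold is 15% (sections 2.1, 3.1, 4.8, 6.1, 9.5). Baseline is the post-saline FEV1 (5.1). The lowest admissible lung function is 80% predicted, with no upper limit (3.3). Baselines above 80% are an assumed range, because the documents give no baseline distribution.

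**The count that the classification feeds.** Section 6.4 assumes that 50% of those screened have an early-phase response and that 50% of these have an LPR: 100 × 0.50 × 0.50 = 25. The plan's figure is reproduced.

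**Notation.** B is post-saline FEV1 in litres, F the post-allergen FEV1 in litres, P the predicted FEV1 in litres, and b = 100 × B/P the baseline in percent predicted. The defined quantity is the relative fall r = 100 × (B − F)/B.

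**Reading 1: percent of post-saline baseline.** The pre-value is 100 and the post-value is 100 × F/B. Post minus pre is 100 × F/B − 100 = −r. For a 15% fall, 85 − 100 = −15. This agrees with the definition apart from the sign.

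**Reading 2: percent predicted.** The drop in points is d = 100 × (B − F)/P = r × b/100. So 15 points correspond to a relative fall of 1500/b, and a 15% relative fall corresponds to 0.15 × b points.

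| Baseline b (% predicted) | Relative fall equal to 15 points (1500/b) | Points recorded for a 15% relative fall (0.15 × b) |
|---|---|---|
| 80 | 18.75% | 12.0 |
| 90 | 16.67% | 13.5 |
| 100 | 15.00% | 15.0 |
| 110 | 13.64% | 16.5 |
| 120 | 12.50% | 18.0 |

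The two rules agree only at exactly 100% predicted. The subtraction is stricter below that and looser above it.

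**One subject.** At 80% predicted, a 16% fall meets section 6.1, but the drop is 0.16 × 80 = 12.8 points, short of 15.

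**In litres, assuming a predicted FEV1 of 4.0 L.** Fifteen points are 0.15 × 4.0 = 0.60 L.

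- At 80% predicted, B = 3.20 L. The relative cut-off is 0.85 × 3.20 = 2.72 L and the points cut-off is 3.20 − 0.60 = 2.60 L. A lowest FEV1 above 2.60 L and up to 2.72 L is an LPR by definition but not by subtraction.
- At 120% predicted, B = 4.80 L. The cut-offs are 0.85 × 4.80 = 4.08 L and 4.80 − 0.60 = 4.20 L. A lowest FEV1 above 4.08 L and up to 4.20 L counts by subtraction but not by definition.

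**Who is affected.** Only subjects whose relative fall lies between 15% and 1500/b. From the 80% floor upwards, 1500/b is at most 18.75%, so any fall of 18.75% or more counts under both rules.

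**Secondary outcome.** The last column of the table applies here too. One and the same relative fall is recorded as 12.0 points at 80% predicted and 16.5 at 110%.

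**The case against.** The strongest reply is that percent of baseline is the natural reading. The sentence just before the subtraction, in both 6.3 and the synopsis, states the endpoint as a fall of at least 15%, and the subtraction is offered as the means of establishing it. Every post-challenge FEV1 threshold elsewhere is relative to baseline: dose escalation and stopping in 5.1, discharge in 4.2 and 4.6, recovery in 4.8 and 9.5, persisting LPR in 9.4. Percent predicted appears only as a floor before the challenge and is never called %FEV1. Subtracting a constant 100 may be no more than loose wording for percent change from baseline. Sections 3.1, 4.8 and 5.1 together already supply threshold, reference and direction, so a careful reader could classify subjects without 6.3. The primary endpoint also carries no hypothesis test.

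Most of this stands. It shows that the harmless reading is open and has good support, and that the definition itself is not in doubt. It does not show that 6.3 states that definition. The statistical section gives an explicit operation on an undefined quantity, and on a credible reading that operation gives a different classification. The absence of a test does not remove the consequence, because the classification is itself the endpoint and ends screening.

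**Conclusion.** The point holds in conditional form and should be fixed. If %FEV1 is percent of post-saline baseline, there is no distortion in size and only a definition is missing. If it is percent predicted, the effective cut-off runs from an 18.75% relative fall at 80% predicted to 13.6% at 110%. Borderline subjects are then misclassified against the protocol's own definition, and the secondary outcome scales with baseline lung function. These figures rest only on the 15% threshold and the baseline value; they do not depend on any standard deviation or response rate.

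A reader might infer two stronger conclusions that the documents do not support.

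- **That 6.3 is wrong however it is read.** It is not: on the percent-of-baseline reading the subtraction returns the defined fall.
- **That the number misclassified can be estimated from the 25.6% ± 9.8% in section 6.4, taken as a normal distribution of relative falls.** That figure is itself stated in the undefined %FEV1, so treating it as relative assumes the answer to the question at issue. Such a distribution would also put about 86% of subjects above a 15% fall, whereas 6.4 expects 0.50 × 0.50 = 25% of those screened to have an LPR. With no baseline distribution given either, the number affected cannot be computed.

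**What to change.** In section 6.3 and in the synopsis, replace the subtraction sentence with:

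percent fall = 100 × (post-saline FEV1 − lowest FEV1 in the 3-10 hour window) / post-saline FEV1, with FEV1 in litres; LPR = percent fall of 15% or more.

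Use the same quantity for the secondary outcome on the largest LPR drop in 6.2 and 6.3, and define %FEV1 or remove it wherever it remains. The formula is correct whichever meaning was intended, ties the reference to the baseline in 5.1, settles the sign, and says which post-allergen value is used.

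The cost is one sentence in two places plus consistent terminology. No new data are needed: section 5.1 already schedules FEV1 after saline and repeatedly out to 10 hours.

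This change does not settle when the 3-10 hour window starts. Sections 2.1 and 6.1 count from the early-phase response, 3.1 from its onset, and 6.3 and the synopsis from the allergen challenge. That is a separate point, and those passages must be reconciled.

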Following the measurement of FEV₁ after the first 7 minute inhalation period, the concentration of saline will be increased from 3% to 4%, provided the FEV₁ decrement is < 10% from the post-bronchodilator value. If the FEV₁ falls between 10-20% of the post bronchodilator value, the test will proceed but the concentration of saline will remain the same. If the FEV₁ falls by > 20% or if troublesome symptoms occur, the nebulization will be discontinued, and albuterol will be immediately available if necessary to relieve symptoms. The same procedure will be followed for the final 7 minute inhalation period using 5% hypertonic saline provided the FEV₁ safety parameters described above have been met. The nebulization is stopped after a total of 21 minutes or earlier if a sputum sample of good quality is obtained (i.e. visible sputum plugs).

5.3. Spirometry:

Standard methodology conforming to the American Thoracic Society/European Respiratory Society guidelines for measurement of spirometry will be used²²

5.4. Methacholine Challenge:

This test measures the responsiveness of the airways to a standard cholinergic bronchoconstriction agent. Methacholine challenge testing is a standard clinical procedure to determine airway reactivity in patients with known or suspected airway disease. Subjects will be asked to limit caffeine on the day of testing. Subjects will inhale 5 breaths from the nebulizer at each concentration starting with saline control. Each breath is started from resting end-expiratory lung volume (Forced Residual Capacity) and continued until a maximum inhalation is reached. Increasing (doubling) concentrations are inhaled until the FEV₁ falls by at least 20% from the post saline value, the highest concentration has been inhaled, or the subject experiences discomfort or anxiety sufficient for the investigator or subject to consider further testing unacceptable. Methacholine concentrations will be 0.075, 0.156, 0.312, 0.625, 1.25, 2.5, 5.0, and 10.0 mg/ml. If subjects experience symptoms that do not rapidly and spontaneously remit at the end of the procedure, he/she will receive 4 puffs of an inhaled bronchodilator (albuterol) MDI. If needed an additional 4 puffs or a nebulizer treatment with standard dose albuterol (0.083mg) will be given. The subject will not be discharged until spirometry levels return to baseline.

5.5. Venipuncture:

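### Section 6.3 names neither a change nor a log scale for methacholine reactivity, although the declared endpoint is a change and the test runs on a doubling ladder

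*Combined protocol and SAP*

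**What the plan says.** Section 6.2, like the synopsis and section 2.2, lists among the secondary outcomes "Change in methacholine reactivity from baseline pre-allergen measurement to 24 hours after allergen challenge". Visit 2 supplies the pre-allergen test and Visit 4 the 24-hour test (section 4.2).

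The analysis is in section 6.3 and is repeated in the synopsis: "we will first use linear regression to determine if there is a linear relationship between baseline sputum IL-1"β (in pg/mL) and a list of outcomes after allergen challenge, with adjustment for confounders that are not named. In that list the outcome appears as "methacholine reactivity defined by the dose required to produce a" FEV1 drop of at least 20%. The word change is absent, and no log or doubling scale is mentioned. The stated remedy for secondary endpoints is: "If the normality assumption is violated or there exists a non-linear relationship, we will calculate the Spearman correlation coefficient". The only sentence in section 6.3 about transforming data stands in the next paragraph, on exploratory endpoints.

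Section 5.4 describes the test: "Increasing (doubling) concentrations are inhaled until the" FEV1 falls by at least 20%, or the test ends for another reason, one being that "the highest concentration has been inhaled". The ladder is given as "Methacholine concentrations will be 0.075, 0.156, 0.312, 0.625, 1.25, 2.5, 5.0, and 10.0 mg/ml". No value is assigned to a subject who finishes it without a 20% fall.

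**The concern.** A test built on doubling steps measures reactivity on a ratio scale: a halving of the provocative concentration means the same wherever the subject starts. A difference in mg/ml does not respect this. It is large for subjects who start high on the ladder and tiny for those who start low, so it largely records the starting point.

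Two things are at stake. A real relation between IL-1β and the shift in reactivity could be missed. And if baseline IL-1β is related to baseline reactivity, the mg/ml change could show an association that is not there. The outcome bears on the IL-1β question that motivates the planned anakinra trials.

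**Working it through.** The plan gives no sample size, power or effect for this analysis; section 6.4 sizes the later anakinra trials. There is therefore no figure to reproduce.

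**1. Step sizes (ladder from section 5.4).** Successive differences are 0.156 - 0.075 = 0.081, then 0.156, 0.313, 0.625, 1.25, 2.5, and 10 - 5 = 5.0 mg/ml. Largest over smallest: 5.0/0.081 = 61.7, or 62-fold. For a two-step shift it is (10 - 2.5)/(0.312 - 0.075) = 7.5/0.237 = 31.6. On the log2 scale the first step is log2(0.156/0.075) = 1.06 and the others are 1.00, so the ratio is about 1.06.

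**2. Does ranking help?** Take two subjects.

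| Visit 2 to Visit 4 | Change, mg/ml | Change, doublings |
|---|---|---|
| 10 to 5 | -5.0 | -1.00 |
| 0.625 to 0.075 | -0.55 | -3.06 |

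The mg/ml ranks call the first shift the larger; the log2 ranks call the second the larger. Spearman on the mg/ml change inherits the wrong order. For the 24-hour value alone, the log preserves order, so Spearman is the same on either scale (simulated mean -0.289 on both).

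**3. Spearman on the change, by scale.** Assumptions, none from the documents: n=50, true correlation of IL-1β with the log2 change -0.5, SD of the change 0.8 doublings, mean shift 1 doubling, ceiling 10 mg/ml.

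| Baseline SD (doublings) | Mean Spearman, mg/ml | Mean Spearman, log2 | Power, mg/ml | Power, log2 |
|---|---|---|---|---|
| 1.0 | -0.33 | -0.47 | 65% | 94% |
| 1.8 | -0.28 | -0.46 | 53% | 94% |

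**4. The section 6.3 sequence applied to the mg/ml change** (linear regression, Spearman if residuals are non-normal). Assumptions: baseline SD 1.8 doublings, mean shift 1 doubling, shift SD 1, lognormal IL-1β, n=50.

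- *Power*, with an effect of 0.5 doubling per SD of log IL-1β and no correlation with baseline reactivity: about 54%, against about 91% for log2 change on log IL-1β.
- *False positives*, with no effect of IL-1β on the shift, by the correlation of IL-1β with the baseline provocative concentration:

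| Correlation | 0 | -0.1 | -0.2 | -0.3 |
|---|---|---|---|---|
| mg/ml change | 5% | 7% | 12% | 22% |

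On the log2 scale the rate at -0.3 is about 5%. Adding test-retest noise of 0.7 doublings (also assumed) lowers the mg/ml rate at -0.3 from about 21% to 12%.

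**The case against.** **The plan never says raw.** It names a dose and is silent on scale, so an analyst could express it in logs. That is right: the defect is an unspecified scale, not a prescribed wrong one. The transformation sentence does not settle it. It sits in the exploratory paragraph, applies only if needed, and names no transform.

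**Section 6.3 may mean the 24-hour value only.** Spearman would then be indifferent to the log, so a blanket statement that the fallback cannot repair the scale would be wrong. But the declared change would go unanalysed, and the result would carry baseline reactivity forward. The text of 6.2 and 6.3 must be reconciled on either reading.

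**Adjustment could remove the bias.** Regressing the mg/ml change with baseline dose as covariate gives about 2% false positives at n=50 and correlation -0.3. However, section 6.3 names no confounders, and a simple Spearman coefficient drops both the adjustment and the promised effect estimate. How often the fallback would be used depends on a normality criterion that the plan does not state.

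**A reader might infer that the plan will produce false, wrong-signed findings, with IL-1β appearing protective.** The documents do not support that. It requires higher IL-1β to go with a lower baseline provocative concentration, and no such correlation is reported; at zero there is no inflation. Rates above 40% at -0.3 would need 100 complete pairs. Section 6.4 sets 100 as a maximum and stops at 25 late-phase responders, and section 9.4 allows sputum induction or methacholine to be skipped.

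**Weight.** This is one of several secondary outcomes in a screening study not sized for it.

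**Conclusion.** The point holds as a mismatch and an omission. The declared endpoint is a change; the analysis text names a dose without change and without a log scale. The 62-fold spread follows from the protocol's own ladder and needs no assumption. The distortion survives Spearman for the mg/ml change, but not for the 24-hour value taken alone.

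The firmer consequence is lost power: about 54% against 91% at n=50, under the assumed spread and effect. That loss does not require any correlation between IL-1β and baseline reactivity. The false-positive consequence is conditional, from about 5% to 22% at n=50 over correlations of 0 to -0.3, and less with measurement noise. The same analysis text also covers eNO and sputum cells per mg, and a reader might extend the point to them. Nothing worked out here bears on those outcomes. The change should be made, but it does not touch the primary endpoint.

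**What to change.** In section 6.3 and the synopsis:

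- Align the methacholine analysis with the declared endpoint: the Visit 2 to Visit 4 change in log2 provocative concentration, reported in doublings.
- Regress it on log IL-1β with the Visit 2 log2 value as covariate.
- State how results beyond the ladder are handled, both no 20% fall at 10 mg/ml and a 20% fall already at the lowest concentration. They could be treated as censored, or given an assigned value with a sensitivity analysis.
- Keep Spearman on the log2 change as a sensitivity analysis.

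The cost is a few sentences. Estimates will read in doublings rather than mg/ml, and a censoring rule has to be chosen. The test procedure stays as it is, and no new data, visits or subjects are needed.
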